#### 5.2.8.1.7 Suicidal risk assessed by the C-SSRS

The C-SSRS is a semi-structured, investigator-rated interview, developed by clinical experts in cooperation with the FDA, assessing both suicidal behavior and suicidal ideation. It does not give a global score, but provides some categorical and some severity information specifically for behavior and ideation.

The C-SSRS interview may be administered by any type of physician, psychologist, clinical social worker, mental health counselor, nurse, or coordinator with C-SSRS training. It has a typical duration of five minutes, and causes only a low burden on subjects. At a minimum, the interview consists of 2 screening questions related to suicidal ideation and 4 related to suicidal behavior, and may be expanded to up to 17 items in case of positive responses. Free text entries are allowed for; the investigator has to directly evaluate the scale and write a report.

The C-SSRS has been widely used in large multinational clinical trials. The C-SSRS will be administered at the screening visit (using the 'screening/baseline' version) with the aim to exclude subjects with active moderate or severe symptomatology within a specified time prior to the screening or baseline visit. The life time history of suicidal ideation and behavior will also be recorded.

After the baseline visit the assessment 'since last visit' will be performed at each clinic or phone visit ('since last visit' version). The investigator is to review positive and negative reports for plausibility and clinical relevance. Doubtful reports may be repeated or reports may be validated by a consulting psychiatrist. If there is a confirmed positive report of suicidal behavior or suicidal ideation type 4 or 5 after start of trial, the investigator is to immediately interview the subject during the clinic visit, and/or is to consult a psychiatrist. If the positive report is confirmed, appropriate actions for the subject's safety have to be initiated.

All C-SSRS reports of suicidal ideation type 4 or 5 and all reports of suicidal behaviour must be reported as separate SAEs by the investigator. For 'Self-injurious behaviour, no suicidal intent' (Type 11) standard AE / SAE reporting rules are to be applied.

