For each negative report (suicidal ideation type 1, 2 or 3) after start of the trial, the investigator is to decide based on clinical judgment whether it represents an adverse event (AE) as defined in the protocol, and if it is considered an AE then it must be reported accordingly.

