Laboratory data will be compared to their reference ranges. Values outside the reference range as well as values defined as possibly clinically significant will be highlighted in the listings. Additionally, differences from baseline will be evaluated.

Vital signs or other safety-relevant data will be assessed with regard to possible on-treatment changes from baseline.

Relevant ECG findings will be reported as AEs.

Suicidality monitoring will be assessed by the C-SSRS questionnaire ([Section 5.2.4](#)). Results will be documented by means of an overall question ("Based on the C-SSRS, has the subject expressed any current suicide ideation or current/past suicide behaviour?" - yes/no). In case this overall question is answered with "yes", the full questionnaire will be included in the clinical trial report. Findings will be reported as AE, the completed forms will be stored at the site.

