#### *Disclaimer:*

*This scale is intended to be used by individuals who have received training in its administration. The questions contained in the Columbia-Suicide Severity Rating Scale are suggested probes. Ultimately, the determination of the presence of suicidal ideation or behavior depends on the judgment of the individual administering the scale.*

*Definitions of behavioral suicidal events in this scale are based on those used in The Columbia Suicide History Form, developed by [name] and [name], Conte Center for the Neuroscience of Mental Disorders (CCNMD), New York State Psychiatric Institute, [name]. (Oquendo M. A., Halberstam B. & Mann J. J., Risk factors for suicidal behavior: utility and limitations of research instruments. In M.B. First [Ed.] Standardized Evaluation in Clinical Practice, pp. 103 -130, 2003.)*

*For reprints of the C-SSRS contact [name]., New York State Psychiatric Institute, [name]; inquiries and training requirements contact [contact]*

© 2008 The Research Foundation for Mental Hygiene, Inc.

Proprietary confidential information © 2019 Boehringer Ingelheim International GmbH or one or more of its affiliated companies

SUICIDAL IDEATION			
Ask questions 1 and 2. If both are negative, proceed to "Suicidal Behavior" section. If the answer to question 2 is "yes", ask questions 3, 4 and 5. If the answer to question 1 and/or 2 is "yes", complete "Intensity of Ideation" section below.		Lifetime: Time He/She Felt Most Suicidal	Past Months
1. Wish to be Dead Subject endorses thoughts about a wish to be dead or not alive anymore, or wish to fall asleep and not wake up. Have you wished you were dead or wished you could go to sleep and not wake up? If yes, describe:		Yes  No 	Yes  No 
2. Non-Specific Active Suicidal Thoughts General non-specific thoughts of wanting to end one's life/commit suicide (e.g., "I've thought about killing myself") without thoughts of ways to kill oneself/associated methods, intent, or plan during the assessment period. Have you actually had any thoughts of killing yourself? If yes, describe:		Yes  No 	Yes  No 

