7.8.5 Others

Physical and neurological examination findings will be reported as relevant medical history/baseline condition (if a condition already exists before first administration of study treatment) or as AE (if condition emerges after first administration of study treatment) and will be summarized as such. No separate listing or analysis of physical or neurological examination findings will be prepared.

Suicidality assessment

Suicidality monitoring will be performed as described in Section 5.2.4 of the CTP, results will only be listed. No further analysis will be prepared. Findings will also be reported as AEs if applicable.

Visual test

Visual test will be performed as described in Section 5.2.3 of the CTP. Abnormal findings during the screening examination will lead to exclusion of the subject.

Any deterioration during the study compared to baseline will be reported as an AE. Results from all measurements will also be listed separately for colour discrimination test, visual acuity test and Amsler grid test and will also be summarized.

Unscheduled measurements of visual tests will be assigned to planned time points in the same way as described above for laboratory data. However, for visual tests, descriptive statistics will be calculated by planned time point based on the last value of the subject at that planned time point (or assigned to that planned time point).

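### The overall C-SSRS yes/no item asks for 'current' ideation while the post-baseline form covers the interval since the last visit, so resolved type 1–3 ideation can be answered 'no' and left out of the report

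*Protocol*

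**What the plan says.** **The form.** Protocol Section 5.2.8.1.7 states: "After the baseline visit the assessment 'since last visit' will be performed at each clinic or phone visit". The version in Appendix 10.1 has a single 'Since Last Visit' column. Its second ideation item carries the same words as the screening version, "without thoughts of ways to kill oneself/associated methods, intent, or plan during the assessment period", so the answer refers to a period and not to the moment of interview.

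**The documented result.** Protocol Section 7.3.4 says: "Results will be documented by means of an overall question". The question is: "Based on the C-SSRS, has the subject expressed any current suicide ideation or current/past suicide behaviour". Only after a 'yes' does the next step follow: "the full questionnaire will be included in the clinical trial report". The paragraph ends: "Findings will be reported as AE, the completed forms will be stored at the site".

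**Low-grade ideation.** Section 5.2.8.1.7 makes type 4–5 ideation and all suicidal behaviour SAEs. For types 1–3 the rule begins "For each negative report (suicidal ideation type 1, 2 or 3) after start of the trial" and leaves it to the investigator's clinical judgment whether the report is an adverse event.

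**The SAP.** Section 7.8.5 says of the suicidality assessment: "results will only be listed. No further analysis will be prepared. Findings will also be reported as AEs if applicable".

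**The concern.** The instrument and the item that summarises it do not share a time window. The form asks what happened since the last visit. The summary item, taken at its word, asks about ideation now. A subject who reports a wish to be dead, or active thoughts that have since passed, has a positive form but may be a 'no' on the item that decides whether the questionnaire reaches the report.

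Suicidality is a listed safety parameter (Protocol Section 2.2.2.2; SAP Section 5.3.2). Section 5.2.4 gives one reason: depression, suicidal ideation and suicide seen in Alzheimer patients on memantine. Section 1.2.1.3 already summarises earlier BI 425809 trials as free of suicidal ideation and behaviour. If this trial is to support a similar statement, a 'no' has to cover the whole exposure interval.

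**Working it through.** No statistical figure is involved. The check sets the rules side by side and follows each kind of event through them.

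1. *Window of the form.* Since the last visit (Section 5.2.8.1.7; Appendix 10.1). The form's duration item starts at a few seconds or minutes, so short episodes are within its scope.
2. *Window of the summary item.* Ideation: current. Behaviour: current or past. The two terms stand in the same sentence, so a literal reader will conclude that past ideation is not asked for. Neither document defines current.
3. *Events traced through the rules:*

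| Event since last assessment | Form | Overall item | Questionnaire in report | AE route |
|---|---|---|---|---|
| Type 4–5 ideation, or any behaviour | yes | yes, or 'no' for resolved ideation read literally | follows the item | SAE, mandatory |
| Type 1–3, present at interview | yes | yes | yes | clinical judgment |
| Type 1–3, resolved; current read as the interval | yes | yes | yes | clinical judgment |
| Type 1–3, resolved; current read as now | yes | **no** | **no** | clinical judgment |

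 Only the last row can be lost from the report. Section 5.2.8.1.7 also calls type 1–3 responses negative reports, which might lead a rater to answer 'no' in the second row.

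4. *Does the AE route close the last row?* Section 7.3.4 says findings will be reported as AEs. Section 5.2.8.1.7 leaves types 1–3 to judgment. SAP Section 7.8.5 says 'if applicable'. The first would close the gap; the other two would not.

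5. *How long is the interval?* As far as the Flow Chart columns can be read in this copy, the C-SSRS marks in Period 2 after first dosing fall at 25:00 (Day 2) and 802:00 (Day 34): 802 − 25 = 777 h, and 777 / 24 = 32.4 days. After treatment they fall at Visit 4 Day 11 and Day 32–37: 32 − 11 = 21 to 37 − 11 = 26 days. Section 5.2.8.1.7 instead requires the scale at each clinic or phone visit. Subjects attend daily for dosing in Period 2, so that rule would cut the first interval to about one day, and the Day 18 phone call would split the second. Section 5.2.4 defers to the Flow Chart. The interval is therefore unresolved in the documents.

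**The case against.** The strongest reply is that the item opens by referring to the C-SSRS, and after baseline that means the since-last-visit form. A rater can reasonably take current to mean the interval just rated, as opposed to lifetime history. The ideation/behaviour contrast also has a parallel in exclusion criteria 24 and 25: lifetime for behaviour, 12 months for ideation. This stands to the extent that a reader might infer that resolved ideation *is* recorded as 'no', and the documents do not support that. They support only that it *can* be, because the term is undefined. Two raters could answer the same form differently.

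A reader might also infer that the yes/no item is the only C-SSRS record. It is not. Completed forms are kept at the site, the investigator must evaluate the scale and write a report, and findings may become AEs. The item is the only C-SSRS result that Section 7.3.4 specifies for documentation, and it controls what enters the report.

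Third, AE questioning takes place every day during up-titration (Flow Chart footnote 9). That helps, but Section 5.2.8.2.1 describes non-specific questions of the how-do-you-feel kind, which do not replace an ideation interview.

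Finally, the practical weight is small. Section 1.2.1.3 reports more than 245 healthy subjects dosed without suicidal ideation or behaviour, and this trial excludes subjects with a relevant history. That stands, and it limits the importance of the point.

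**Conclusion.** The point holds as a defect of wording and of consistency between sections. An episode is absent from the reported C-SSRS results only if four things coincide: it is type 1–3, it has resolved by the interview, the rater reads current literally, and the investigator does not judge it an AE. Type 4–5 ideation and all behaviour still surface as SAEs.

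No rate of loss can be given. It would need the duration of episodes, which the documents do not supply, and the C-SSRS interval, on which they conflict. A reader might take the 32.4-day gap as established; it rests on broken Flow Chart columns and disagrees with Section 5.2.8.1.7. Few events are expected in 16 healthy subjects, and no pharmacokinetic estimate is affected. The case for acting is that the correction is cheap and that otherwise a line of 'no' answers cannot be read as absence of ideation during exposure.

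**What to change.** 1. For post-baseline assessments, reword the overall item in Protocol Section 7.3.4 to ask for *any suicidal ideation (type 1–5) or suicidal behaviour since the last C-SSRS assessment*. Tying it to the last C-SSRS, not the last visit, makes it independent of how the schedule is settled. The screening item needs no lifetime-ideation wording: that would add historical entries without improving on-treatment capture.
2. After a 'yes', record the most severe ideation type and an approximate date, and list both by treatment under SAP Section 7.8.5.
3. Reconcile Protocol Sections 5.2.8.1.7 and 7.3.4 and SAP Section 7.8.5 on how type 1–3 reports reach the trial report, and reconsider the label 'negative' for them.
4. Reconcile the each-clinic-or-phone-visit rule in Section 5.2.8.1.7 with the C-SSRS times in the Flow Chart.

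*Cost.* One reworded item, two short fields used only after a 'yes', and small text changes in the protocol and SAP. Items 1 and 2 need no new assessment: the completed form already holds the ideation type, and the date can be asked at interview or taken from the free-text description. A few low-grade entries may appear in the listing and need comment.

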# COLUMBIA-SUICIDE SEVERITY RATING SCALE (C-SSRS)

Since Last Visit

Version 1/14/09

*Posner, K.; Brent, D.; Lucas, C.; Gould, M.; Stanley, B.; Brown, G.; Fisher, P.; Zelazny, J.; Burke, A.; Oquendo, M.; Mann, J.*

#### *Disclaimer:*

*This scale is intended to be used by individuals who have received training in its administration. The questions contained in the Columbia-Suicide Severity Rating Scale are suggested probes. Ultimately, the determination of the presence of suicidal ideation or behavior depends on the judgment of the individual administering the scale.*

*Definitions of behavioral suicidal events in this scale are based on those used in The Columbia Suicide History Form, developed by [name] and [name], Conte Center for the Neuroscience of Mental Disorders (CCNMD), New York State Psychiatric Institute, [name]. (Oquendo M. A., Halberstam B. & Mann J. J., Risk factors for suicidal behavior: utility and limitations of research instruments. In M.B. First [Ed.] Standardized Evaluation in Clinical Practice, pp. 103 -130, 2003.)*

*For reprints of the C-SSRS contact [name]., New York State Psychiatric Institute, [name]; inquiries and training requirements contact [contact]*

*© 2008 The Research Foundation for Mental Hygiene, Inc.*

Proprietary confidential information © 2019 Boehringer Ingelheim International GmbH or one or more of its affiliated companies

SUICIDAL IDEATION		Since Last Visit																		

Ask questions 1 and 2. If both are negative, proceed to "Suicidal Behavior" section. If the answer to question 2 is "yes", ask questions 3, 4 and 5. If the answer to question 1 and/or 2 is "yes", complete "Intensity of Ideation" section below.
																				

1. Wish to be Dead Subject endorses thoughts about a wish to be dead or not alive anymore, or wish to fall asleep and not wake up. Have you wished you were dead or wished you could go to sleep and not wake up?
 
If yes, describe:
		Yes  No 																		

2. Non-Specific Active Suicidal Thoughts General, non-specific thoughts of wanting to end one's life/commit suicide (e.g., "I've thought about killing myself") without thoughts of ways to kill oneself/associated methods, intent, or plan during the assessment period. Have you actually had any thoughts of killing yourself?
 
If yes, describe:
		Yes  No 																		

3. Active Suicidal Ideation with Any Methods (Not Plan) without Intent to Act Subject endorses thoughts of suicide and has thought of at least one method during the assessment period. This is different than a specific plan with time, place or method details worked out (e.g., thought of method to kill self but not a specific plan). Includes person who would say, "I thought about taking an overdose but I never made a specific plan as to when, where or how I would actually do it...and I would never go through with it." Have you been thinking about how you might do this?
 
If yes, describe:
		Yes  No 																		

4. Active Suicidal Ideation with Some Intent to Act, without Specific Plan Active suicidal thoughts of killing oneself and subject reports having some intent to act on such thoughts, as opposed to "I have the thoughts but I definitely will not do anything about them." Have you had these thoughts and had some intention of acting on them?
 
If yes, describe:
		Yes  No 																		

5. Active Suicidal Ideation with Specific Plan and Intent Thoughts of killing oneself with details of plan fully or partially worked out and subject has some intent to carry it out. Have you started to work out or worked out the details of how to kill yourself? Do you intend to carry out this plan?
 
If yes, describe:
		Yes  No 																		
INTENSITY OF IDEATION																				

The following features should be rated with respect to the most severe type of ideation (i.e., 1-5 from above, with 1 being the least severe and 5 being the most severe).
 
Most Severe Ideation:
 
  
 Type # (1-5)	Description of Ideation	Most Severe	
   
  
Frequency How many times have you had these thoughts? (1) Less than once a week (2) Once a week (3) 2-5 times in week (4) Daily or almost daily (5) Many times each day
 	—	
 
  
Duration When you have the thoughts, how long do they last? (1) Fleeting - few seconds or minutes (4) 4-8 hours/most of day (2) Less than 1 hour/some of the time (5) More than 8 hours/persistent or continuous (3) 1-4 hours/a lot of time
 	—	
 
  
Controllability Could/can you stop thinking about killing yourself or wanting to die if you want to? (1) Easily able to control thoughts (4) Can control thoughts with a lot of difficulty (2) Can control thoughts with little difficulty (5) Unable to control thoughts (3) Can control thoughts with some difficulty (0) Does not attempt to control thoughts
 	—	
 
  
Deterrents Are there things - anyone or anything (e.g., family, religion, pain of death) - that stopped you from wanting to die or acting on thoughts of committing suicide? (1) Deterrents definitely stopped you from attempting suicide (4) Deterrents most likely did not stop you (2) Deterrents probably stopped you (5) Deterrents definitely did not stop you (3) Uncertain that deterrents stopped you (0) Does not apply
 	—	
 
  
Reasons for Ideation What sort of reasons did you have for thinking about wanting to die or killing yourself? Was it to end the pain or stop the way you were feeling (in other words you couldn't go on living with this pain or how you were feeling) or was it to get attention, revenge or a reaction from others? Or both? (1) Completely to get attention, revenge or a reaction from others (4) Mostly to end or stop the pain (you couldn't go on living with the pain or how you were feeling) (2) Mostly to get attention, revenge or a reaction from others (5) Completely to end or stop the pain (you couldn't go on living with the pain or how you were feeling) (3) Equally to get attention, revenge or a reaction from others and to end/stop the pain (0) Does not apply
 	—	
  
		Type # (1-5)	Description of Ideation	Most Severe	
Frequency How many times have you had these thoughts? (1) Less than once a week (2) Once a week (3) 2-5 times in week (4) Daily or almost daily (5) Many times each day
		—	
Duration When you have the thoughts, how long do they last? (1) Fleeting - few seconds or minutes (4) 4-8 hours/most of day (2) Less than 1 hour/some of the time (5) More than 8 hours/persistent or continuous (3) 1-4 hours/a lot of time
		—	
Controllability Could/can you stop thinking about killing yourself or wanting to die if you want to? (1) Easily able to control thoughts (4) Can control thoughts with a lot of difficulty (2) Can control thoughts with little difficulty (5) Unable to control thoughts (3) Can control thoughts with some difficulty (0) Does not attempt to control thoughts
		—	
Deterrents Are there things - anyone or anything (e.g., family, religion, pain of death) - that stopped you from wanting to die or acting on thoughts of committing suicide? (1) Deterrents definitely stopped you from attempting suicide (4) Deterrents most likely did not stop you (2) Deterrents probably stopped you (5) Deterrents definitely did not stop you (3) Uncertain that deterrents stopped you (0) Does not apply
		—	
Reasons for Ideation What sort of reasons did you have for thinking about wanting to die or killing yourself? Was it to end the pain or stop the way you were feeling (in other words you couldn't go on living with this pain or how you were feeling) or was it to get attention, revenge or a reaction from others? Or both? (1) Completely to get attention, revenge or a reaction from others (4) Mostly to end or stop the pain (you couldn't go on living with the pain or how you were feeling) (2) Mostly to get attention, revenge or a reaction from others (5) Completely to end or stop the pain (you couldn't go on living with the pain or how you were feeling) (3) Equally to get attention, revenge or a reaction from others and to end/stop the pain (0) Does not apply
		—	—
Type # (1-5)	Description of Ideation	Most Severe																		

Frequency How many times have you had these thoughts? (1) Less than once a week (2) Once a week (3) 2-5 times in week (4) Daily or almost daily (5) Many times each day
		—																		

Duration When you have the thoughts, how long do they last? (1) Fleeting - few seconds or minutes (4) 4-8 hours/most of day (2) Less than 1 hour/some of the time (5) More than 8 hours/persistent or continuous (3) 1-4 hours/a lot of time
		—																		

Controllability Could/can you stop thinking about killing yourself or wanting to die if you want to? (1) Easily able to control thoughts (4) Can control thoughts with a lot of difficulty (2) Can control thoughts with little difficulty (5) Unable to control thoughts (3) Can control thoughts with some difficulty (0) Does not attempt to control thoughts
		—																		

Deterrents Are there things - anyone or anything (e.g., family, religion, pain of death) - that stopped you from wanting to die or acting on thoughts of committing suicide? (1) Deterrents definitely stopped you from attempting suicide (4) Deterrents most likely did not stop you (2) Deterrents probably stopped you (5) Deterrents definitely did not stop you (3) Uncertain that deterrents stopped you (0) Does not apply
		—																		

Reasons for Ideation What sort of reasons did you have for thinking about wanting to die or killing yourself? Was it to end the pain or stop the way you were feeling (in other words you couldn't go on living with this pain or how you were feeling) or was it to get attention, revenge or a reaction from others? Or both? (1) Completely to get attention, revenge or a reaction from others (4) Mostly to end or stop the pain (you couldn't go on living with the pain or how you were feeling) (2) Mostly to get attention, revenge or a reaction from others (5) Completely to end or stop the pain (you couldn't go on living with the pain or how you were feeling) (3) Equally to get attention, revenge or a reaction from others and to end/stop the pain (0) Does not apply
		—																		

Version 1/14/09

Proprietary confidential information © 2019 Boehringer Ingelheim International GmbH or one or more of its affiliated companies

SUICIDAL BEHAVIOR (Check all that apply, so long as these are separate events; must ask about all types)		Since Last Visit

Actual Attempt: A potentially self-injurious act committed with at least some wish to die, as a result of act. Behavior was in part thought of as method to kill oneself. Intent does not have to be 100%. If there is any intent/desire to die associated with the act, then it can be considered an actual suicide attempt. There does not have to be any injury or harm, just the potential for injury or harm. If person pulls trigger while gun is in mouth but gun is broken so no injury results, this is considered an attempt. Inferring Intent: Even if an individual denies intent/wish to die, it may be inferred clinically from the behavior or circumstances. For example, a highly lethal act that is clearly not an accident so no other intent but suicide can be inferred (e.g., gunshot to head, jumping from window of a high floor/story). Also, if someone denies intent to die, but they thought that what they did could be lethal, intent may be inferred.
 
Have you made a suicide attempt?
 
Have you done anything to harm yourself?
 
Have you done anything dangerous where you could have died?
 
What did you do?
 
Did you _____ as a way to end your life?
 
Did you want to die (even a little) when you _____?
 
Were you trying to end your life when you _____?
 
Or did you think it was possible you could have died from _____?
 
Or did you do it purely for other reasons / without ANY intention of killing yourself (like to relieve stress, feel better, get sympathy, or get something else to happen)? (Self-Injurious Behavior without suicidal intent)
 
If yes, describe:
		
Yes  No 
 
Total # of Attempts _____
 
Yes  No 


Has subject engaged in Non-Suicidal Self-Injurious Behavior?
 
Interrupted Attempt: When the person is interrupted (by an outside circumstance) from starting the potentially self-injurious act (if not for that, actual attempt would have occurred). Overdose: Person has pills in hand but is stopped from ingesting. Once they ingest any pills, this becomes an attempt rather than an interrupted attempt. Shooting: Person has gun pointed toward self, gun is taken away by someone else, or is somehow prevented from pulling trigger. Once they pull the trigger, even if the gun fails to fire, it is an attempt. Jumping: Person is poised to jump, is grabbed and taken down from ledge. Hanging: Person has noose around neck but has not yet started to hang - is stopped from doing so.
 
Has there been a time when you started to do something to end your life but someone or something stopped you before you actually did anything?
 
If yes, describe:
		
Yes  No 
 
Total # of interrupted _____
 
Yes  No 

Aborted Attempt: When person begins to take steps toward making a suicide attempt, but stops themselves before they actually have engaged in any self-destructive behavior. Examples are similar to interrupted attempts, except that the individual stops him/herself, instead of being stopped by something else.
 
Has there been a time when you started to do something to try to end your life but you stopped yourself before you actually did anything?
 
If yes, describe:
		
Yes  No 
 
Total # of aborted _____
 
Yes  No 


Preparatory Acts or Behavior: Acts or preparation towards imminently making a suicide attempt. This can include anything beyond a verbalization or thought, such as assembling a specific method (e.g., buying pills, purchasing a gun) or preparing for one's death by suicide (e.g., giving things away, writing a suicide note).
 
Have you taken any steps towards making a suicide attempt or preparing to kill yourself (such as collecting pills, getting a gun, giving valuables away or writing a suicide note)?
 
If yes, describe:
		
Yes  No 
 
Yes  No 

Suicidal Behavior: Suicidal behavior was present during the assessment period?
 
Suicide:
		
Yes  No 
 
Yes  No 


Answer for Actual Attempts Only
 
Actual Lethality/Medical Damage:
 
 
0. No physical damage or very minor physical damage (e.g., surface scratches).
 
1. Minor physical damage (e.g., lethargic speech; first-degree burns; mild bleeding, sprains).
 
2. Moderate physical damage; medical attention needed (e.g., conscious but sleepy, somewhat responsive; second-degree burns; bleeding of major vessel).
 
3. Moderately severe physical damage, medical hospitalization and likely intensive care required (e.g., comatose with reflexes intact; third-degree burns less than 20% of body; extensive blood loss but can recover, major fractures).
 
4. Severe physical damage, medical hospitalization with intensive care required (e.g., comatose without reflexes; third-degree burns over 20% of body; extensive blood loss with unstable vital signs; major damage to a vital area).
 
5. Death
 
 
Potential Lethality: Only Answer if Actual Lethality=0 Likely lethality of actual attempt if no medical damage (the following examples, while having no actual medical damage, had potential for very serious lethality: put gun in mouth and pulled the trigger but gun fails to fire so no medical damage; laying on train tracks with oncoming train but pulled away before run over).
 
0 = Behavior not likely to result in injury 1 = Behavior likely to result in injury but not likely to cause death 2 = Behavior likely to result in death despite available medical care
		
Most Lethal Attempt Date: _____
 
Enter Code _____
 
Enter Code _____

